9.2.2 Selection criteria

The study population will consist of all patients, newly initiated on Rivaroxaban or Phenprocoumon with an NVAF diagnosis meeting the following inclusion and exclusion criteria

Inclusion criteria:

- First dispense date of Rivaroxaban (15mg or 20mg - PZN based) or Phenprocoumon (PZN based) between January 1, 2012 and December 31, 2015
- At least two verified outpatient diagnoses or one inpatient diagnosis (main or secondary diagnosis) of NVAF (ICD-10 GM I48.0/ I48.1/I48.2/I48.9) in the individual time frame of 4 quarters before the index date (pre-index period) or within the index quarter
- Patients will be required to have 4 quarters of enrollment for the assessment of baseline characteristics and be observable and insured in the database for at least one day after their individual index date (post-index period)
- ≥ 18 years of age

Exclusion criteria:

- Patients with valvular AF [4 quarters prior to the index date] (see Table 5)
- Pregnancy [4 quarters prior to index date]

- Malignant cancers [4 quarters prior to the index date or “condition after”] (see Table 10)
- Transient cause of AF [4 quarters prior to index date] (see Table 5)
- Patients with VTE (pulmonary embolism or DVT) [60 days before index] (see Table 10)
- Patients with major surgery defined as hip or knee replacement [60 days before index] (see Table 10)
- Prescriptions of OACs (Rivaroxaban, VKA, Dabigatran, Apixaban) before index date [4 quarters prior to index date] (see Table 3, Table 4)
- Patients receiving more than one anticoagulant substance (Apixaban, Dabigatran, Rivaroxaban or Phenprocoumon) or more than one dosage of a substance on the index date (see Table 3, Table 4)
- *For sensitivity analysis* ([see data analysis section](#)) : Patient with any of the events defined in the combined endpoints [4 quarters prior to index date or “condition after”] (see Table 6)
- Patients with dialysis [4 quarters prior to index date] (see Table 10)

[figure not shown]

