9.3 Variables

9.3.1 Baseline characteristics

Baseline period:

365 days prior to index date for hospital diagnoses and prescriptions and four quarters prior to the index quarter for ambulatory diagnosis. This period will be used to determine whether patients have an NVAF diagnosis, to verify that patients are new users and to assess baseline demographic and clinical characteristics of the patients included in the study population.

The following demographics will be reported for each cohort:

- Gender
- Age
- Age group
 - 18-65, 65-74, ≥ 75

The following clinical characteristics will be reported for each cohort:

- 4-quarter Charlson comorbidity index (CCI)
- CKD, which is important as risk of adverse events among patients receiving NOACs tends to differ according to renal function)
- CHADS₂ score, including Congestive heart failure, hypertension, age, diabetes, stroke
- CHA₂DS₂-Vasc score
- HASBLED score, as measurable without lab values
- Prior non-CNS systemic embolism
- Prior oral anticoagulant use (expected to be 0 with 180-day covariate look back)
- Other relevant co-morbidities:
 - Congestive heart failure
 - DVT
 - Essential hypertension
 - Diabetes mellitus
 - Pulmonary embolism
 - Unstable angina
 - Hyperthyroidism
 - Functional dyspepsia
 - Renal failure

- Other cardiovascular drugs:
 - Antiarrhythmics
 - Beta blockers
 - ACE inhibitors
 - ARBs
 - Calcium channel blockers
 - Diuretics
 - Anti-platelet drug classes
 - NSAIDS

Stroke risk score CHADS₂ and CHA₂DS₂-VASc

Stroke risk scores in the individual pre-index period of 4 quarters before the index quarter with defined risk factors and corresponding ICD-10-GM codes including heart failure, hypertension, age groups, diabetes mellitus, stroke/TIA/embolism, vascular disease and gender (listed in Annex 2, Table 7).

To include Health Care Proxies

- Number of hospitalizations in the baseline period
- Number of unique medications in the baseline period

Comorbidities

Presence of relevant comorbidities e.g. hemorrhagic diathesis due to anticoagulants and antibodies, coagulopathy, hyperthyroidism, etc. (see Annex 2, Table 6) in the inpatient sector (main and secondary diagnoses) or in the outpatient sector (verified diagnoses and in addition “condition after diagnoses” for stroke, bleedings and MI) in the patient’s medical history in the individual pre-index period of 4 quarters before the index quarter will be assessed.

Co-medications

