Chronic renal insufficiency stage III	categorical	Ambulatory verified diagnoses in the four quarters prior to the index quarter as well as primary and secondary hospital discharge diagnoses within the 365 days before or on the index date will be used assess whether patients suffered from a chronic renal insufficiency, stage I. Chronic renal insufficiency, stage III will be defined using the ICD-10 GM code N18.3.
Chronic renal insufficiency stage IV	categorical	Ambulatory verified diagnoses in the four quarters prior to the index quarter as well as primary and secondary hospital discharge diagnoses within the 365 days before or on the index date will be used assess whether patients suffered from a chronic renal insufficiency, stage I. Chronic renal insufficiency, stage IV will be defined using the ICD-10 GM code N18.4.
Chronic renal insufficiency stage V	categorical	Ambulatory verified diagnoses in the four quarters prior to the index quarter as well as primary and secondary hospital discharge diagnoses within the 365 days before or on the index date will be used assess whether patients suffered from a chronic renal insufficiency, stage I. Chronic renal insufficiency, stage V will be defined using the ICD-10 GM code N18.5.

Other chronic renal insufficiency	categorical	Ambulatory verified diagnoses in the four quarters prior to the index quarter as well as primary and secondary hospital discharge diagnoses within the 365 days before or on the index date will be used assess whether patients suffered from other chronic renal insufficiency. Other chronic renal insufficiency will be defined using the ICD-10 GM code N18.8.
Unspecified chronic renal insufficiency	categorical	Ambulatory verified diagnoses in the four quarters prior to the index quarter as well as primary and secondary hospital discharge diagnoses within the 365 days before or on the index date will be used assess whether patients suffered from an unspecified renal insufficiency. Unspecified chronic renal insufficiency will be defined using the ICD-10 GM code N18.9.
Diabetes	categorical	Ambulatory verified diagnoses in the four quarters prior to the index quarter as well as primary and secondary hospital discharge diagnoses within the 365 days before or on the index date will be used assess whether patients suffered from diabetes mellitus. Diabetes mellitus will be defined using the ICD-10 GM code E10.*-E14.*.

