9.7.1.2 Primary and secondary objectives

The incidence rate and corresponding confidence intervals of the primary and secondary endpoints will be estimated as the number of events per 100 person years (% per year). Cox proportional hazard regression will be used to estimate unadjusted and adjusted hazard ratios (multivariate adjusted as well as 1:1 propensity matched). For all models, hazard ratios (HRs), 95% confidence intervals (CIs) and all other regression coefficients will be reported.

Kaplan-Meier curves will be generated to evaluate the time-to-first event associated with the initial treatment.

Rivaroxaban will be compared to Phenprocoumon. Hence, Phenprocoumon will be the reference category in the analysis. A subset of the variables depicted in Table 2 which were selected on an empirical basis, will be included as covariates in the Cox proportional hazards model.

Propensity Score Matching

In this study, we will additionally use propensity score matching. The propensity score will be calculated as the predicted probability of exposure (i.e. probably of receiving Rivaroxaban), given all that is known about a patient (i.e. patient characteristics and covariates).

The probability itself will be derived from a multivariate logistic regression using the parameters thought to act as confounding variables. The propensity score act as a “balancing score” in that all factors that contribute to the score are expected to be independent between treatment groups if the patient population is matched on propensity score and a stratified table of patient characteristics is examined. That is, after propensity score matching all other factors included in the score are expected to be balanced between the two treatment groups. This will minimize confounding by observed baseline covariates by removing any potential relationship between cofounders and exposure group.

In this study, we will estimate propensity scores from all measured factors noted above. These factors will be entered into a logistic regression model, with the factors as the independent variables (with no further variable selection) and the treatment as the dependent variable. From the resulting model, we will predict probability of treatment for each patient; this probability of treatment will be each patient’s estimated propensity score.

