Diabetes mellitus	1	1	E11/E10/ E12	Type 2 diabetes mellitus/ Type 1 diabetes mellitus/ Diabetes mellitus in combination with malnutrition Non-traumatic intracerebral hemorrhage/ Cerebral infarction/stroke/ Sequelae of cerebrovascular disease/ Other venous embolism and thrombosis/ Transient cerebral ischemic attacks and related syndromes/ Arterial embolism and thrombosis/ Acute vascular disorders of intestine/ Ischemia and infarction of kidney/ Retinal vascular occlusions Acute myocardial infarction/ recurrent myocardial infarction/ Certain current complications following myocardial infarction/ Other peripheral vascular diseases
Stroke/TIA/embolism	2	2	I61/I63/I64/ I69/I82/G45 /I74/K55.0/ N28.0/H34	
Vascular disease (prior myocardial infarction/peripheral artery disease/aortic plaque)	0	1	I21/I22/I23/ I73	
Female gender	0	1	-	

Table 8 – Comorbidities included in the Charlson Comorbidity Index (CCI) and modified comorbidity index

Conditions	ICD-10 GM code	Assigned weights CCI	Assigned weights modified comorbidity index
Myocardial Infarction	I21, I22, I252	1	1
Congestive heart failure	I43, I50, I099, I110, I130, I132, I255, I420, I425, I 426, I427, I428, I429, P290	1	0
Peripheral vascular disease	I70, I71, I731, I738, I739, I771, I790, I792, K551, K558, K559, Z958, Z959	1	1
Cerebrovascular disease	G45, G46, I60, I61, I62, I63, I64, I65, I66, I67, I68, I69, H340	1	0
Dementia	F00, F01, F02, F03, G30, F051, G311	1	1
Chronic pulmonary disease	J40, J41, J42, J43, J44, J45, J46, J47, J60, J61, J62, J63, J64, J65, J66, J67, I278, I279, J684, J701, J703	1	1
Connective tissue disease	M05, M32, M33, M34, M06, M315, M351, M353, M360	1	1
Ulcer disease	K25, K26, K27, K28	1	1
Mild liver disease	B18, K73, K74, K700, K701, K702, K703, K709, K717, K713, K714, K715, K760, K762, K763, K764, K768, K769, Z944	1	0
Diabetes	E100, E101, E106, E108, E109, E110, E111, E116, E118, E119, E120, E121, E126, E128, E129, E130, E131, E136, E138, E139, E140, E141, E146, E148, E149	1	1
Hemiplegia	G81, G82, G041, G114, G801, G802, G830, G831, G832, G833, G834, G839	2	2
Moderate or severe renal disease	N18, N19, N052, N053, N054, N055, N056, N057, N250, I120, I131, N032, N033, N034, N035, N036, N037, Z490, Z491, Z492, Z940, Z992	2	0
Diabetes with end organ damage	E102, E103, E104, E105, E107, E112, E113, E114, E115, E117, E122, E123, E124, E125, E127, E132, E133, E134, E135, E137, E142, E143, E144, E145, E147	2	2

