Any tumor	C00, C01, C02, C03, C04, C05, C06, C07, C08, C09, C10, C11, C12, C13, C14, C15, C16, C17, C18, C19, C20, C21, C22, C23, C24, C25, C26, C30, C31, C32, C33, C34, C37, C38, C39, C40, C41, C43, C45, C46, C47, C48, C49, C50, C51, C52, C53, C54, C55, C56, C57, C58, C60, C61, C62, C63, C64, C65, C66, C67, C68, C69, C70, C71, C72, C73, C74, C75, C76, C81, C82, C83, C84, C85, C88, C90, C91, C92, C93, C94, C95, C96, C97	2	2
Moderate or severe liver disease	K704, K711, K721, K729, K765, K766, K767, I850, I859, I864, I982	3	0
Metastatic solid tumor or AIDS	C77, C78, C79, C80, B20, B21, B22, B24	6	6

Table 9 – Operationalization HAS-BLED Score

Criteria	ICD-10 GM code
Hypertension	I10.*, I11.*, I12.*, I13.*, I14.*, I15.*
Renal disease	N18.*, N19.*
Cirrhosis	K70.3, K71.7, K74.*
Stroke	I63.*
Major bleeding event	Primary or secondary hospital discharge of ICD-10 codes as listed in Table 11
Alcohol use	F10.*
Non-steroidal anti-inflammatory drug	M01A*
Antiplatelet agents	B01AC*
Age >65	

Table 10 – Definition of comorbidities

Comorbidity	ICD-10-GM code / OPS Code
Hemorrhagic diathesis due to anticoagulants and antibodies	D68.3
Coagulopathy, not specified	D68.9
Hyperthyroidism	E05
Diabetes mellitus	E10-E14
Hyperlipidemia	E78.0-E78.5
Cerebral transitory ischemia and related problems	G45
Essential hypertension	I10
Angina pectoris	I20
Myocardial infarction	I21-I22
Other acute ischaemic heart disease	I24
Chronic ischaemic heart disease	I25
Pulmonary embolisms	I26
Heart failure	I50
Intracerebral hemorrhage	I61
Other non-traumatic intracranial bleeding	I62
Cerebral infarction	I63
Stroke, not referred to as bleeding or infarction	I64
Hemorrhage or intracranial bleeding or cerebral infarction or stroke	I61-I64
Peripheral vascular disease, not specified	I73.9
Embolism and thrombosis of unspecified artery	I74.9
Deep thrombosis on leg and pelvic veins	I80-I82 without I80.0
Functional dyspepsia	K30
Hepatic insufficiency	K72
Renal insufficiency	N17-N18
Chronic renal disease, stage 1	N18.1
Chronic renal disease, stage 2	N18.2
Chronic renal disease, stage 3	N18.3
Chronic renal disease, stage 4	N18.4
Chronic renal disease, stage 5	N18.5
Cancer	C00-C97
Gastrointestinal bleeding*	K92.0.-K92.2
Dialysis	Z49.0, Z49.1, Z49.2
Hip or knee replacement procedure	OPS 5820, OPS 5821, OPS 5822, OPS 5823

Table 11 – Definition of major bleeding events for HAS-BLED Score

Primary or secondary hospital discharge diagnosis ICD-10-GM code	ICD-10-GM code

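### The dialysis exclusion in Table 10 omits Z99.2, which the protocol's own renal list in Table 8 contains, so patients coded only that way stay in the cohorts

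*Protocol*

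**What the plan says.** Protocol section 9.2.2 lists as an exclusion "Patients with dialysis [4 quarters prior to index date] (see Table 10"). The criterion is thus operationalised entirely by that table. In Annex 2, Table 10, the dialysis row holds three diagnosis codes: "Z49.0, Z49.1, Z49.2". No procedure code is given for dialysis, although the next row of the same table defines joint replacement by procedure: "OPS 5820, OPS 5821, OPS 5822, OPS 5823".

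In Annex 2, Table 8, the Charlson row for moderate or severe renal disease ends with "Z490, Z491, Z492, Z940, Z992". It contains the three Table 10 codes and also Z992.

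Section 9.3.1 explains why renal status is collected: the "risk of adverse events among patients receiving NOACs tends to differ according to renal function". The renal covariates in Table 2 are the N18 stages, for example "Chronic renal insufficiency, stage V will be defined using the ICD-10 GM code N18.5". Table 2 has no dialysis covariate. For matching, section 9.7.1.2 says "we will estimate propensity scores from all measured factors noted above".

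Section 9.7 states that no separate SAP will be written, and Annex 1 lists no stand-alone documents. As the protocol stands, the Table 10 row is the operative rule.

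**The concern.** The protocol decides to remove dialysis patients from both cohorts, but the code list that carries out the decision is narrower than a renal list printed elsewhere in the same annex. A patient whose dialysis is recorded over the four quarters only as Z99.2 is not caught. The same holds for a patient identifiable only from a billed procedure.

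If such patients have a different rate of stroke or intracranial hemorrhage and are unevenly divided between the drugs, they distort the comparison on both primary endpoints, to the extent that the covariates do not absorb the difference. The final cohort would also not be the one that the selection criteria describe.

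**Working it through.** The plan states no figure on this point, so there is none to reproduce. The check has three parts.

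**1. Code lists side by side (Annex 2).**
- Table 10, dialysis: Z490, Z491, Z492.
- Table 8, moderate or severe renal disease, Z codes only: Z490, Z491, Z492, Z940, Z992.
- In Table 8 but not in Table 10: Z940 and Z992. Only Z992 is at issue here. The protocol prints it without a label; its meaning is the standard ICD one.
- No other section widens the dialysis definition.

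**2. What the covariates see for a patient with Z99.2 and no Z49 code.**
- CKD stage covariates (Table 2): informative only if an N18 code is also present. N18.5 does not distinguish stage 5 with dialysis from stage 5 without.
- HAS-BLED renal item (Table 9): N18 and N19 only.
- Full Charlson index (Tables 2 and 8): Z992 is scored, with weight 2, the same weight as any N18 code.
- Modified comorbidity index (Table 8): renal disease has weight 0.
- Propensity score: takes all measured factors without further selection, so the full Charlson index and the CKD stages enter.
- Adjusted Cox model: takes an empirically chosen subset of Table 2, so a renal term is not guaranteed.

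Adjustment is therefore present but partial. A dialysis patient can be matched to a patient with non-dialysis renal disease.

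**3. Illustrative size.** Let p be the share of an arm made up of missed dialysis patients and RR their event rate relative to other patients. An arm's average rate is its base rate × (1 + p(RR − 1)). Without adjustment, the hazard ratio is therefore multiplied by

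(1 + p_riva(RR − 1)) / (1 + p_phen(RR − 1)).

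Both p and RR are assumptions; the documents give neither. With p_riva = 0:

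| p_phen | RR = 2 | RR = 3 | RR = 4 |
|---|---|---|---|
| 0.1% | 1/1.001 = 0.999 | 1/1.002 = 0.998 | 1/1.003 = 0.997 |
| 0.5% | 1/1.005 = 0.995 | 1/1.010 = 0.990 | 1/1.015 = 0.985 |
| 1% | 1/1.010 = 0.990 | 1/1.020 = 0.980 | 1/1.030 = 0.971 |
| 2% | 1/1.020 = 0.980 | 1/1.040 = 0.962 | 1/1.060 = 0.943 |

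- RR = 5 with p_phen = 2% would give 1/1.08 = 0.926.
- If rivaroxaban has half the prevalence (1% against 2%), RR = 4 gives 1.03/1.06 = 0.972.
- If the imbalance is reversed (2% on rivaroxaban, none on phenprocoumon), RR = 4 gives 1.06, in the other direction.
- With about 30,000 phenprocoumon patients (section 9.5), 2% means 600 missed patients and 0.1% means 30.

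**Scale.** Section 9.5 gives 17,000 and 30,000 patients. With its ROCKET-AF stroke rates as printed, and one person-year per patient assumed, events are 17,000 × 0.0134 + 30,000 × 0.0126 = 228 + 378 = 606. The standard error of the log hazard ratio is 1/√(606 × 0.362 × 0.638) = 0.085, so the 95% interval is the estimate divided and multiplied by exp(1.96 × 0.085) = 1.18. Every factor in the table lies well inside that interval.

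**The case against.** A reader might infer that long-term dialysis patients as a group remain in the study. They do not. Anyone with a Z49.0, Z49.1 or Z49.2 code in the four quarters is excluded, and a single such code is enough. Only patients with no Z49 code throughout that period can remain, and nothing in the documents says how many there are; there may be almost none.

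A reader might also infer a bias in favour of rivaroxaban. That needs the missed patients to be concentrated on phenprocoumon, which no section states. The protocol also gives no reason for the dialysis exclusion, so a confounding rationale is inference.

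Table 8 serves a different purpose from Table 10. It is a comorbidity score row based on published coding algorithms, and it also covers N18, N19 and Z940. Two lists for two constructs are not in themselves a contradiction, and the omission of Z99.2 need not have been deliberate. Adjustment is also more than nominal, since the full Charlson index scores Z992 and enters the propensity score with the CKD stages. Finally, a definition by diagnosis codes alone is legitimate, and nothing shows that it is insensitive without procedure codes.

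These objections stand as limits on size, direction and wording. They do not explain why a criterion meant to remove dialysis patients leaves out a dialysis code printed in the same annex.

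**Conclusion.** The point holds in a limited form. The dialysis exclusion is defined more narrowly than the protocol's own renal code list, and patients recorded with Z99.2 but no Z49 code stay in the cohorts against the stated criterion. The covariates adjust for them only in part, because the Charlson index gives Z99.2 the same weight as any N18 code and there is no dialysis covariate.

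The number and arm split of these patients are not given, so the size and direction of any bias are unknown. Under the assumed prevalences (0.1% to 2%) and risk ratios (2 to 4), the unadjusted factor on the hazard ratio is about 0.94 to 1.00 if all are on phenprocoumon, and closer to 1 if both arms contain them. Adjustment would be expected to reduce it further. The change is worth making because it costs almost nothing and makes the criterion do what it says. The documents do not show a material bias, and they do not show that omitting procedure codes is an error.

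**What to change.** Add Z99.2 to the dialysis row of Annex 2, Table 10, and apply the row identically to both arms over the four quarters before the index date. Report by arm how many patients the added code removes; that supplies the figure now missing and shows whether the issue mattered. If the narrower list was intended, say why and report by arm how many included patients carry Z99.2.

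Optionally, add dialysis procedure codes (inpatient OPS, outpatient EBM). Section 9.4 says the database holds both, and Table 10 already uses OPS codes for another exclusion.

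The cost is one table row and a code-list edit before the cohort is drawn. The downside is the loss of a few patients whom the protocol already meant to exclude.

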Phenprocoumon	Attenuation	H03BA	Thiouracile
Rivaroxaban	Boost	G01AF02	Clotrimazol
Rivaroxaban	Boost	G01AF05	Econazol
Rivaroxaban	Boost	J02AC01	Fluconazol
Rivaroxaban	Boost	J02AC02	Itraconazol
Rivaroxaban	Boost	G01AF11	Ketoconazol
Rivaroxaban	Boost	J02AB02	Ketoconazol
Rivaroxaban	Boost	G01AF17	Oxiconazol
Rivaroxaban	Boost	J02AC04	Posaconazol
Rivaroxaban	Boost	J02AC03	Voriconazol
Rivaroxaban	Boost	J05AE	Proteasehemmer
Rivaroxaban	Boost	B01	Antithrombotische Mittel
Rivaroxaban	Boost	M01A	Nichtsteroidale Antiphlogistika und Antirheumatika
Rivaroxaban	Boost	R05GB07	Erythromycin, Kombinationen
Rivaroxaban	Boost	J01FA01	Erythromycin
Rivaroxaban	Boost	S01AA17	Erythromycin
Rivaroxaban	Attenuation	J04AB02	Rifampicin
Rivaroxaban	Attenuation	J04AM02	Rifampicin und Isoniazid
Rivaroxaban	Attenuation	J04AM05	Rifampicin, Pyrazinamid und Isoniazid
Rivaroxaban	Attenuation	J04AM06	Rifampicin, Pyrazinamid, Ethambutol und Isoniazid
Rivaroxaban	Attenuation	N03AA02	Phenobarbital
Rivaroxaban	Attenuation	N03AF01	Carbamazepin
Rivaroxaban	Attenuation	N03AB02	Phenytoin

Table 13 – Definition of co-medications

Medication	ATC
Anticoagulation therapy	
VKA	B01AA
Phenprocoumon	B01AA04
Thrombin inhibitors	B01AE
Rivaroxaban	B01AF01, B01AX06
Apixaban	B01AF02, B01AX08
ASA	B01AC06
Other anticoagulants	B01AB or B01AX or B01AC excl. B01AC06
None	No B01A
Antiarrhythmic drugs	
Class I: Sodium channel blockers	C01BA01 Chinidin C01BA02 Procainamid C01BA05 Ajmalin C01BA03 Disopyramid C01BC03 Propafenon C01BA08 Prajmalin C01BB01 Lidocain N03AB02 Phenytoin C01BB02 Mexiletin C01BB04 Aprindin C01BB03 Tocainid C01BC04 Flecainid C01BC07 Lorcaïnid
Class II: Beta-blockers	C07AB04 Acebutolol C07AB03 Atenolol C07AB02 Metoprolol C07AA05 Propranolol C07AA07 Sotalol
Class III: Potassium channel blockers	C01BD01 Amiodaron C01BD05 Ibutilid C07AA07 Sotalol C01BD07 Dronedaron
Class IV: Calcium antagonists	C08DA01 Verapamil C08DA02 Gallopamil C08DB01 Diltiazem
Digitalis	C01AA05 Digoxin C01AA04 Digitoxin
Other	C01EB10 Adenosin A12CC* Magnesium Parasympatholytika (A03BA01/G04BD15 Atropin, C01CX10 Ipratropiumbromid) R03C* Sympathomimetics for systemic use C01CA24 Epinehrin C01CA03 Norepinephrin R03CB03 Orciprenaline

C01EB10 Ivabradine (If-channel-blocker)

Other medications

ACE-inhibitors	C09A ACE-inhibitors, pure
	C09B ACE-inhibitors, combinations
ATII-antagonists	C09C Angiotensin II antagonists, pure
	C09D Angiotensin II antagonists, combinations
Beta-blocker	C07A Beta-adrenoceptor-antagonists
Calcium-antagonists	C08D Selective calcium channel blocker with main effect on the heart
Diuretics	C03 Diuretics
Nitrates	C01DA Organic nitrates
Statins	C01AA HMG-CoA-reductase inhibitor
Antidiabetic medications	A10 Antidiabetics
Thyroid medications	H03A Thyroid preparations
NSAIDs	M01A* Antiinflammatory and antirheumatic products, non-steroids

Table 14 – Definition of anticoagulants

Medication	ATC
Anticoagulation therapy	
VKA	B01AA
Phenprocoumon	B01AA04
Thrombin inhibitor	B01AE
Rivaroxaban	B01AF01, B01AX06
Apixaban	B01AF02, B01AX08
ASA	B01AC06
Other anticoagulants	B01AB or B01AX or B01AC excl. B01AC06

Table 15 – Availability of variables of interest

	Variable	Germany
Patient's characteristics	Age	yes
	Gender	yes
	Death	yes
Diagnosis	Atrial fibrillation, stroke risk scores CHADS ₂ and CHA ₂ DS ₂ -VASc, comorbidities including cardiovascular events and GI-bleedings	ICD-10-GM
Prescription drugs	Xarelto® and VKA and other medications of interest (other anticoagulants, antiarrhythmics, digitalis, other medications such as diuretics, statins etc.)	ATC/PZN

Table 16 – Demographic characteristics before matching

Age groups	Rivaroxaban patients (n, %)			VKA patients (n, %)		
	Female	Male	Total	Female	Male	Total
0-19						
20-29						
30-39						
40-49						
50-59						
60-64						
65-74						
≥75						
Total						

Table 17 – Demographic characteristics - statistics before matching

Age	Mean	Standard deviation	Minimum	Median	Maximum
Rivaroxaban patients					
Female					
Male					
Total					
VKA patients					
Female					
Male					
Total					

Table 18 – Type of AF diagnosis before matching

ICD-10-GM code	Type of AF	Rivaroxaban patients (n, %)	VKA patients (n, %)
I48.0	Paroxysmal		
I48.1	Persistent		
I48.2	Permanent		
I48.3	Typical		
I48.4	Atypical		
I48.9	Unknown		
Total			

Table 19 – CHADS₂ risk score before matching

CHADS₂ risk score value	Rivaroxaban patients (n, %)	VKA patients (n, %)
0		
1		
2		
3		
4		
5		
6		

Table 20 – CHA₂DS₂-VASc risk score before matching

CHA₂DS₂-VASc risk score value	Rivaroxaban patients (n, %)	VKA patients (n, %)
0		
1		
2		
3		
4		
5		
6		
7		
8		
9		

Table 21 – Co-morbidities before matching

Comorbidity	Rivaroxaban patients (n, %)	VKA patients (n, %)
Hemorrhagic diathesis due to anticoagulants and antibodies Coagulopathy, not specified Hyperthyroidism Diabetes mellitus Hyperlipidemia Cerebral transitory ischemia and related problems Essential hypertension Angina pectoris Myocardial infarction Other acute ischemic heart disease Chronic ischemic heart disease Pulmonary embolisms Heart failure Intracerebral hemorrhage Other non-traumatic intracranial bleeding Cerebral infarction Stroke, not referred to as bleeding or infarction Hemorrhage or intracranial bleeding or cerebral infarction or stroke Peripheral vascular disease, not specified Deep thrombosis on leg and pelvic veins Functional dyspepsia Hepatic insufficiency Renal insufficiency Chronic renal disease, stage 1 Chronic renal disease, stage 2 Chronic renal disease, stage 3 Chronic renal disease, stage 4 Chronic renal disease, stage 5 Cancer Gastrointestinal bleeding*		

Table 22 – Co-mediations before matching

	Rivaroxaban patients (n, %)	VKA patients (n, %)
Anticoagulation therapy		
VKA		
Thrombin inhibitors		
Rivaroxaban		
Apixaban		
ASA		
Other anticoagulants		
None		
Antiarrhythmic drugs		
Class I		
Class II		
Class III		
Class IV		
Digitalis		
Other		
Other medications		
ACE-inhibitors		
ATII-antagonists		
Beta-blocker		
Calcium-antagonists		
Diuretics		
Nitrates		
Statines		
Antidiabetic medications		
Thyroid medications		

Table 23 – Demographic characteristics after matching

Age groups	Rivaroxaban cohort (n, %)			VKA cohort (n, %)		
	Female	Male	Total	Female	Male	Total
0-19						
20-29						
30-39						
40-49						
50-59						
60-64						
65-74						
≥75						
Total						

Table 24 – Demographic characteristics - statistics after matching

Age	Mean	Standard deviation	Minimum	Median	Maximum
Rivaroxaban cohort					
Female					
Male					
Total					
VKA cohort					
Female					
Male					
Total					

Table 25 – Type of AF diagnosis after matching

ICD-10-GM code	Type of AF	Rivaroxaban cohort (n, %)	VKA cohort (n, %)
I48.0	Paroxysmal		
I48.1	Persistent		
I48.2	Permanent		
I48.3	Typical		
I48.4	Atypical		
I48.9	Unknown		
Total			

Table 26 – CHADS₂ risk score after matching

CHADS₂ risk score value	Rivaroxaban cohort (n, %)	VKA cohort (n, %)
0		
1		
2		
3		
4		
5		
6		

Table 27 – CHA₂DS₂-VASc risk score after matching

CHA₂DS₂-VASc risk score value	Rivaroxaban cohort (n, %)	VKA cohort (n, %)
0		
1		
2		
3		
4		
5		
6		
7		
8		
9		

Table 28 – Comorbidities after matching

Comorbidity	Rivaroxaban cohort (n, %)	VKA cohort (n, %)
Hemorrhagic diathesis due to anticoagulants and antibodies		
Coagulopathy, not specified		
Hyperthyroidism		
Diabetes mellitus		
Hyperlipidemia		
Cerebral transitory ischemia and related problems		
Essential hypertension		
Angina pectoris		
Myocardial infarction		
Other acute ischemic heart disease		
Chronic ischemic heart disease		
Pulmonary embolisms		

Heart failure Intracerebral hemorrhage Other non-traumatic intracranial bleeding Cerebral infarction Stroke, not referred to as bleeding or infarction Hemorrhage or intracranial bleeding or cerebral infarction or stroke Peripheral vascular disease, not specified Deep thrombosis on leg and pelvic veins Functional dyspepsia Hepatic insufficiency Renal insufficiency Chronic renal disease, stage 1 Chronic renal disease, stage 2 Chronic renal disease, stage 3 Chronic renal disease, stage 4 Chronic renal disease, stage 5 Cancer	
---	--

Table 29 – Co-medications after matching

	Rivaroxaban cohort (n, %)	VKA cohort (n, %)
Anticoagulation therapy		
VKA		
Thrombin inhibitors		
Rivaroxaban		
Apixaban		
ASA		
Other anticoagulants		
None		
Antiarrhythmic drugs		
Class I		
Class II		
Class III		
Class IV		
Digitalis		
Other		
Other medications		

ACE-inhibitors
 ATII-antagonists
 Beta-blocker
 Calcium-antagonists
 Diuretics
 Nitrates
 Statines
 Antidiabetic medications
 Thyroid medications

Table 30 – Standardized Differences before and after matching

Demographic and characteristics	Standardized differences before matching	Standardized differences before matching
Age		
Gender		
Type of atrial fibrillation		
I48.0		
I48.1		
I48.2		
I48.3		
I48.4		
I48.9		
Stroke risk score CHA2DS2 VASc		
1		
...		
9		
No of Comorbidities		
1		
... >10		
Separate Comorbidites		
Cancer		
...		

Table 31 – Primary endpoints after matching

Description	Rivaroxaban cohort (n, %)	VKA cohort (n, %)	HR (HR, CI)
Ischemic stroke			
Intracranial hemorrhage (ICH)			

Table 32 – Composite cerebral benefit endpoint after matching

Description	Rivaroxaban cohort (n, %)	VKA cohort (n, %)	HR (HR, CI)
Composite cerebral			

benefit (Ischemic stroke and Intracranial hemorrhage (ICH))

Table 33 – Single events of the composite effectiveness endpoint after matching

Description	Rivaroxaban cohort (n, %)	VKA cohort (n, %)	HR (HR, CI)
Ischemic stroke			
Transient ischemic attack (TIA)			
Systemic embolism			
subarachnoid hemorrhage (safety)			
intracerebral hemorrhage (safety)			
other and unspecified nontraumatic intracranial hemorrhage (safety)			
Composite effectiveness endpoint			

Table 34 – Composite cerebral benefit endpoint after matching

Description	Rivaroxaban cohort (n, %)	VKA cohort (n, %)	HR (HR, CI)
Composite cerebral benefit			

Table 35 – Summary statistics for hospitalizations (overall) after matching

All-cause hospitalizations (number)	n (%) of patients	Sum	Mean	Standard deviation	Minimum	Median	Maximum
Rivaroxaban cohort							
VKA cohort							

Table 36 – Summary statistics of the duration of hospitalizations (overall) after matching

Days	Sum	Mean	Standard deviation	Minimum	Median	Maximum
Rivaroxaban cohort						
VKA cohort						

Table 37 – Co-mediations (anticoagulants) after matching

	Rivaroxaban cohort (n, %)	VKA cohort (n, %)
Anticoagulation therapy		
VKA		
Thrombin		
Rivaroxaban		
Apixaban		
ASA		
Other anticoagulants		

